7.5.2.2 Categorical Endpoints

The binary secondary endpoints defined in this study are:

- Proportion of subjects who achieve a minimally clinically important improvement (of at least 3 points) in the ESSDAI at all measured time points up to Day 169 in the full population, among those with stimulated whole salivary flow of at least 0.1mL/min at both screening and

Double-blind analysis over time

The binary endpoints given above at each timepoint (at which endpoint is collected) up to Day 169 will be analyzed as specified in Section 7.1.4. The modified ITT population will be used. Missing values will be imputed as non-responders. In addition, the secondary binary efficacy endpoints will also be analyzed for 2 subgroups:

- subgroup of subjects with stimulated whole salivary flow of at least 0.1mL/min at both screening and baseline
- subgroup of subjects with stimulated whole salivary flow of less than 0.1mL/min at screening or baseline.

The subgroup analyses mentioned in the 2 bullets above will only be provided if there are at least 10 subjects in each treatment group in each of the subgroups.

The logistic model for these subgroup analysis will not include the stimulated salivary flow stratification variable.

The response rate (%) and 95% CI over time will be plotted for each treatment group up to Day 169 for the secondary binary endpoints.

Analysis from Day 1 up to Day 365

The binary endpoints given above at each timepoint in double-blind and open-label period up to Day 365 will be summarized by a point estimate for the response rate and corresponding 95 % CI for the 2 original randomized treatment arms. No treatment differences will be provided for any timepoints during the open-label period.

The modified ITT population will be used. Missing values will be imputed as non-responders. In addition, the secondary binary efficacy endpoints will also be analyzed for 2 subgroups:

- subgroup of subjects with stimulated whole salivary flow of at least 0.1mL/min at both screening and baseline
- subgroup of subjects with stimulated whole salivary flow of less than 0.1mL/min at screening or baseline.

The subgroup analyses mentioned in the 2 bullets above will only be provided if there are at least 10 subjects in each treatment group in each of the subgroups.

The response rate (%) and 95% CI over time will be plotted for each treatment group during the double-blind and open-label periods up to Day 365 for the secondary binary endpoints.

7.5.2.3 Subgroup Analyses

All analyses described in this section will be performed on the modified ITT Analysis Population. All subgroups will be defined based on the data as entered on the CRF; no IWRS will be used for any subgroup analysis.

Table 7.5.2.3-1 shows the subgroups of interest for analyses of the primary efficacy endpoint of Change from Baseline at Day 169 (ESSDAI). The analysis will be using the methods described in Section 7.1.3 for each level of each subgroup, except that all stratification variables and the baseline ESSDAI day-by-day interaction will be removed from the model for this subgroup analysis. If the value of the grouping variable cannot be determined for a subject, the subject will be excluded from the corresponding subgroup analysis. Only subgroups with at least 10 patients in both treatment arms will be considered.

A forest plot showing per subgroup the estimates per treatment group and the treatment differences will be provided. The sample size for each treatment group in the subgroup will be presented along with the adjusted mean change from baseline (with 95% CI) and the treatment difference (with 95% CI).

Table 7.5.2.3-1: Subgroups of Interest

Subgroup factor	Categories
Age	< 65 Years Old
	≥ 65 Years Old
Baseline Weight	< 60kg
	60 - 100kg
	> 100kg
Gender	Male
	Female
Race	White
	Black
	Asian
	Other
Geographic Region	North America
	South America
	Asia
	Europe
	ROW
	Baseline Hydroxychloroquine use as recorded in CRF
	No
Baseline oral corticosteroid use as recorded in CRF	Yes
	No
Baseline Stimulated Salivary Flow as recorded in CRF	< 0.1mL/min
	≥ 0.1mL/min

Table 7.5.2.3-1: Subgroups of Interest

Subgroup factor	Categories
Japan as recorded in CRF	Yes
	No
ESSDAI categories at Day 1	Low < 5
	Moderate $5 \leq \text{ESSDAI} \leq 13$
	High ≥ 14

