3.3.1 Inclusion Criteria

1. Signed Written Informed Consent

- a. Subject is willing to participate and has signed informed consent.

2. Target Population

- a. Subjects must meet the proposed 2015 ACR/EULAR Classification Criteria for SS (Sjögren’s Syndrome) ([Appendix 3](#)), as specified for pSS (primary Sjögren’s Syndrome).

- i. If a prior labial salivary or parotid gland biopsy was performed, information will be reported in the CRF and the report should be obtained for the source documents.
- b. Subjects should have pSS that is refractory to symptomatic or local therapy (eg, NSAIDs).
- c. ESSDAI \geq 5 at screening.
- d. Positive anti-SSA/Ro at screening.
- e. Stimulated salivary flow of at least 0.1 mL/min at screening and randomization in at least 124 subjects (72%). Enrollment of subjects with less than 0.1 mL/min of stimulated salivary flow at screening and/or randomization may be closed after 48 of such subjects are randomized.
- f. Subject Re-enrollment: This study permits the re-enrollment of a subject that has discontinued the study as a pre-treatment failure (ie, a “screen failure”, the subject has not been randomized / has not been treated). If re-enrolled, the subject must be re-consented and will receive a new PID.

3. Age and Reproductive Status

- a. Males and Females, ages \geq 18 (or age of majority).
- b. Women of childbearing potential (WOCBP) must have a negative serum or urine pregnancy test (minimum sensitivity 25 IU/L or equivalent units of HCG) within 24 hours prior to the start of study drug.
- c. Women must not be breastfeeding.
- d. Women of childbearing potential (WOCBP) must agree to follow instructions for method(s) of contraception for the duration of treatment with study drug(s) (abatacept/placebo) plus 5 half-lives of study drug (70 days) plus 30 days (duration of ovulatory cycle) for a total of 100 days post-treatment completion.
- e. Males who are sexually active with WOCBP must agree to follow instructions for method(s) of contraception for the duration of treatment with study drug(s) (abatacept/placebo) plus 5 half-lives of the study drug (70 days) plus 90 days (duration of sperm turnover) for a total of 160 days post-treatment completion. In addition, male subjects must be willing to refrain from sperm donation during this time.

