5 SAMPLE SIZE AND POWER

A sample size of 172 patients (86 per arm) will achieve 98% power to detect a treatment difference of 3 in changes from baseline in ESSDAI at Day 169 between the abatacept and placebo group using a two-sided t-test with a significance level (alpha) of 0.05 and assuming a common SD of 4.8. The sample size of 86 patients per arm will achieve 90% power to detect a treatment difference of 1 in change from baseline in ESSPRI at Day 169 assuming a common SD of 2. Taking into account the hierarchical procedure (described in [Section 7.5](#)), a sample size of 86 patients per arm will achieve an overall power of at least 88.2% (98% multiplied by 90%) to detect both a treatment difference of 3 in mean change from baseline in ESSDAI and a difference of 1 in change from baseline in ESSPRI at Week 24 (Day 169).

The treatment differences of 3 for ESSDAI and 1 for ESSPRI correspond to the minimal clinically important improvement (MCII) for ESSDAI and ESSPRI, the key endpoints that address the major signs and symptoms of this disease. Estimates of the SD of mean change from baseline in ESSDAI derived from published results, range from 3.6 to 6.3. Estimates of the SD of mean change from baseline in ESSPRI derived from published results range from 1.7 to 2.2.

In addition, the power to detect a treatment difference in mean change from baseline of 0.165mL/min in salivary flow in subjects with stimulated whole salivary flow at baseline of at least 0.1mL/min is 91%, assuming a SD of 0.275 and for a sample size of 62 subjects per arm with a residual salivary flow of at least 0.1mL/min at screening and baseline. Taking into account the hierarchical procedure, a sample size of 86 patients per arm will achieve an overall power of at least 80.3 % (98% multiplied by 90% multiplied by 91%) to detect a treatment difference of 3 in mean change from baseline in ESSDAI, a difference of 1 in mean change from baseline in ESSPRI and a treatment difference of 0.165mL/min in mean change from baseline in salivary flow (in subjects with stimulated whole salivary flow at screening and at baseline of at least 0.1mL/min) at Week 24 (Day 169).

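### The subgroup forest plot for Day 169 ESSDAI gives the treatment effect within each level but no between-level difference in effects, so it does not directly show whether effects differ

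*SAP*

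**What the plan says.** SAP 7.5.2.3 sets the subgroup analyses of change in ESSDAI at Day 169. Table 7.5.2.3-1 lists ten factors with two to five levels each.

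- **Model:** "The analysis will be using the methods described in Section 7.1.3 for each level of each subgroup, except that all stratification variables" and the baseline-by-day term are removed.
- **Size rule:** "Only subgroups with at least 10 patients in both treatment arms will be considered".
- **Output:** "A forest plot showing per subgroup the estimates per treatment group and the treatment differences will be provided". Each row also carries the sample size per arm, and both the adjusted means and the treatment difference have 95% confidence intervals.

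The visible text of 7.5.2.3 has no treatment-by-subgroup term and no between-level difference. Every interaction in SAP 7.1.3 is with day. SAP 7.5 allows no subgroup p-values.

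Two other parts of the SAP bear on this. Section 7.1.3 defines three sequential back-up models with spatial power covariance for computational problems. Section 7.5.2.1 separately analyses ESSDAI in two flow subgroups defined by flow at both screening and baseline. For those fits it removes the flow stratification variable; by its wording the other stratification main effects and baseline-by-day stay in. It too shows no between-level contrast in its visible text, though parts of that section are redacted.

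Protocol 3.3.1 asks for at least 124 subjects with flow of 0.1 mL/min or more at screening and randomization. Enrolment of the low-flow group "may be closed after 48 of such subjects are randomized".

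**The concern.** A subgroup plot is read to learn whether the treatment effect differs between levels. Under this plan each level is estimated alone, and the quantity that answers the question, the difference between the level effects with its uncertainty, is not produced. The common substitute is to note which intervals exclude zero. With unequal levels that mostly reflects sample size: a level with few subjects can miss zero-exclusion although its effect equals that of the larger level.

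Salivary flow is the natural example. It is a randomization factor, ESSDAI by flow is a named secondary endpoint, and the enrolment rule makes the two levels unequal by design. A chance pattern in which abatacept seems to work only with residual flow could be taken as a finding, with nothing beside it to show how imprecise the comparison is.

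**Working it through.** **Inputs from the documents.** SAP 5 plans the primary comparison "using a two-sided t-test with a significance level (alpha) of 0.05 and assuming a common SD of 4.8". The planned difference is 3 with 86 per arm, and published SDs "derived from published results, range from 3.6 to 6.3". SAP 5 takes the larger flow group "for a sample size of 62 subjects per arm with a residual salivary flow of at least 0.1mL/min at screening and baseline". The smaller is 172 − 124 = 48, or 24 per arm at 1:1.

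**Assumptions.** The same true difference in both levels; no missing data (the documents give no dropout rate); an unadjusted t-test at Day 169; and the 62/24 split applied to the flow row of 7.5.2.3. That row is labelled by baseline flow only, so its real sizes may differ.

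**Reproducing the plan's figure.** Power comes from the noncentral t with 2n − 2 degrees of freedom and noncentrality d / (SD × √(2/n)). For n = 86, d = 3, SD 4.8 this is 3 / 0.732 = 4.10, and power is 98.3%. The SAP states: "A sample size of 172 patients (86 per arm) will achieve 98% power to detect a treatment difference of 3 in changes from baseline". It reproduces.

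**Power within each flow level (d = 3, SD 4.8).**
- 62 per arm: SE = 4.8 × √(2/62) = 0.862; power p1 = 0.932.
- 24 per arm: SE = 4.8 × √(2/24) = 1.386; power p2 = 0.563.

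**Chance that exactly one interval excludes zero.** p1(1 − p2) + p2(1 − p1) = 0.407 + 0.038 = 0.445. The normal approximation gives 42.9%, and simulation of 200,000 trials gives 44.6%. Nearly all of it is the larger level excluding zero while the smaller does not.

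**Range.**

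| Case | Exactly one interval excludes zero |
|---|---|
| d = 3, SD 3.6, 62/24 | 18–20% |
| d = 3, SD 4.8, 62/24 | 43–45% |
| d = 3, SD 6.3, 62/24 | 56–57% |
| d = 2, SD 4.8, 62/24 | 56% |
| d = 3, SD 4.8, 43/43 | 30% |
| d = 3, SD 4.8, 76/10 (smallest level allowed) | 72% |

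**What drives it.** With one pooled error variance for both levels, the 44.5% becomes 43.4%. The low power at 24 per arm is the cause; separate fitting contributes almost nothing.

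**The missing contrast.** The levels contain different subjects, so SE = √(0.862² + 1.386²) = 4.8 × √(2/62 + 2/24) = 1.63, and 1.96 × 1.63 = 3.2 ESSDAI points. In the simulation, with identical effects, its 95% interval excludes zero in 5.0% of trials. In 41% of trials exactly one level excludes zero while the contrast does not.

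**The case against.** The strongest reply is that the SAP never tells anyone to read the plot by zero-exclusion. It gives estimates, intervals and sample sizes and withholds p-values, which is a cautious presentation. Under the same assumptions the two intervals fail to overlap in only about 0.7% of trials. The level estimates are independent, so a reader can work out a two-level contrast by hand. All this stands, and it keeps the point small. It does not remove the point: a pre-specified analysis should supply the comparison it invites, and hand calculation becomes awkward for race or region.

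A reader might infer more than the documents support:

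- **That separate fitting makes identical effects look different in 44% of trials.** It does not. The figure depends on one definition of looking different, stays at 43.4% with a pooled variance, and moves widely with the SD. The subgroup model adjusts for baseline ESSDAI, so the residual SD may be below 4.8; at an illustrative 4.2 the figure is 33%.
- **That 62/24 is the plan's own split for this row.** It is not: those sizes rest on flow at screening and baseline, 124 is a minimum, and 48 is a point at which enrolment may close. A smaller low-flow level would raise the figure.
- **That an unstructured covariance is forced onto as few as 20 subjects.** The 7.1.3 back-up models cover computational failure. What is unsettled is whether they are applied level by level, which could leave rows of one plot with different covariance structures.
- **That randomization factors are dropped from every flow analysis.** Section 7.5.2.1 appears to keep the others, and redactions there prevent a claim that the plan is silent throughout.

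**Conclusion.** The point holds in a limited form. SAP 7.5.2.3 estimates the Day 169 effect separately in each level and plans no between-level difference, so the plot does not directly answer whether effects differ. The 44% illustrates how misleading zero-exclusion can be under the stated assumptions. It is not a property of separate fitting, and the fix will not lower it. What the fix adds is the right comparison: for the assumed flow split, a contrast with a 95% interval of about ±3.2 points and a 5% false-signal rate. An interval wider than the planned effect of 3 also tells readers plainly that the trial cannot settle subgroup differences of that size.

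Severity is low. The output is exploratory, and no primary or key secondary conclusion depends on it.

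**What to change.** For each factor, fit one model to the modified ITT subjects in levels that meet the 10-per-arm rule, so that sparse levels do not enter the fit.

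- **Terms:** the 7.1.3 model with its stratification main effects, less the one that duplicates the factor, plus subgroup, subgroup-by-day, treatment-by-subgroup and treatment-by-subgroup-by-day.
- **Back-up models:** apply the 7.1.3 sequence once per factor, so that all rows of a factor share one covariance structure.
- **Output:** add to the forest plot the Day 169 between-level difference in treatment effect with its 95% interval and no p-value. State a reference level for factors with more than two levels.

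The cost is a change of SAP wording and one model per factor in place of one per level. The main drawback is an assumed common covariance across levels. The separate fits can stay as a check; at minimum, the contrast can then be computed from the independent level estimates as their difference, with SE √(SE₁² + SE₂²). With ten factors, some contrasts will exclude zero by chance: if there were ten independent ones, the probability of at least one is 1 − 0.95¹⁰ = 40%. A sentence labelling them descriptive should go with the plot.

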7.6 Safety

The safety analysis endpoints described in this section are considered as secondary endpoints. For their analysis, there will be no statistical testing of group differences.

Analysis of all safety data will follow the BMS standard safety data conventions³ and abatacept program safety conventions⁴.

All summaries of safety parameters during the Double-Blind Treatment Period will be provided by treatment groups. All safety assessments will be included in the summary tables if the onset date is on or after the first dose date and up to 56 days post the last dosing day in the Double-Blind Treatment Period or the first dosing date in the open-label period, whichever occurs first. Presentations for the Double-Blind Treatment Period will be provided by “as treated” treatment group for the as-treated analysis population, unless otherwise specified.

These safety endpoints will also be summarized during the cumulative abatacept period (from the first day of abatacept treatment in the study up to 56 days after the last abatacept treatment in the study) for the cumulative abatacept population. For the cumulative abatacept population all subjects will be combined in one group.

7.6.1 Adverse Events

All AEs are coded and grouped into Preferred Terms (PT) by System Organ Class (SOC), using the latest approved version of the Medical Dictionary for Regulatory Activities (MedDRA) at the time of database lock. Listings and summaries will be based on the resulting SOC and PTs.

AEs during the Double-Blind Treatment Period will be included in the frequency tabulations if they occur while a subject is on study medication during the Double-Blind Treatment Period and up to 56 days post the last dosing day in Double-Blind Treatment Period or the first dosing date in the open-label period, whichever occurs first. These AE summaries will be based on proportions, which represent the number of subjects experiencing the AEs divided by the number of subjects who received at least 1 dose of study medication.

AEs during the cumulative abatacept period will be included in the frequency tabulations if they occur while a subject is on abatacept up to 56 days after the last abatacept treatment in the study. These AE summaries will be based on proportions, which represent the number of subjects experiencing the AEs divided by the number of subjects who received at least 1 abatacept dose during the study. For the cumulative abatacept summaries all subjects will be combined in one group.

For summaries by SOC and PT, SOCs will be sorted by decreasing frequency then alphabetically and within SOC, PTs will be sorted by decreasing frequency then alphabetical. For summaries by PT, PTs will be sorted by decreasing frequency then alphabetically.

All adverse events listings will indicate the unique subject identifier, age, gender, current treatment, the date of onset, the date of resolution, day of onset relative to the start of treatment, action taken, investigator's assessment of severity and relationship to study drug.

Laboratory AEs are laboratory changes identified by the investigator as AEs and thus reported on the AE pages of the eCRF and included in the summaries of AEs.

All serious and non-serious adverse events with onset during the Double-Blind Treatment Period will be summarized by SOC, PT, and treatment group. All serious and non-serious adverse events with onset during the cumulative abatacept period will be summarized by SOC and PT overall (in one treatment group). These summaries will be produced for:

- all adverse events
- adverse events related to the study drug, as determined by the investigator
- adverse events leading to discontinuation of study medication
- most common related adverse events (reported in 2% of subjects or more in any treatment group)
- most common adverse events (reported in 5% of subjects or more in any treatment group)
- all serious adverse events
- all serious adverse events related to the study drug
- adverse events by intensity

7.6.2 Adverse Events of Interest

The following adverse events of special interest will be summarized by PT and treatment groups during the Double-Blind Treatment and cumulative abatacept periods. A subject listing will also be provided.

7.6.2.1 Infections

The summaries for the SOC: *Infections and infestations* are included in the summaries of all adverse events detailed above. A by subject listing with the infections will also be provided

7.6.2.2 Malignancy

All events in the MedDRA Maintenance and Support Services Organization (MSSO) malignancies Structured MedDRA Query (SMQ) list occurring during each study period (Double-Blind Treatment Period, Cumulative Abatacept Period) will be reported separately by study period. These events will be summarized by preferred term within each study period separately and will also be listed.

7.6.2.3 Autoimmune Disorders

The frequency of pre-specified autoimmune disorders (defined using a BMS custom Autoimmune Disorder SMQ) occurring during each study period (Double-Blind Treatment Period, Cumulative Abatacept Period) will be provided separately for each study period. Autoimmune disorders will also be summarized by intensity and a listing of all reported autoimmune disorders will be provided.

7.6.2.4 Injection Reactions

- 1) Systemic Injection Reactions are defined as pre-specified systemic AEs (such as hypersensitivity reactions) occurring during the first 24 hours after SC injection.
- 2) Local Injection Site Reactions (LISR) are defined as those AEs that occur at the site of SC injection. A pre-specified list of MedDRA codes for Local Injection Site Reaction (LISR) events of interest will be used to identify the local injection site reactions.

The frequency of pre-specified systemic injections (1) and local injection site reactions (2) (defined using a BMS custom SMQ) occurring during each study period (Double-Blind Treatment Period, Cumulative Abatacept Period) will be provided for (1) and (2) separately and for each study period separately. These AEs will also be summarized by intensity and a listing of all these reported AEs will be provided

In addition to the summary of LISR, the following 5 AEs PTs will be summarized separately for the each study period (Double-Blind Treatment Period or Cumulative Abatacept Period): *Injection Site Erythema, Injection Site Pain, Injection Site Pruritus, Injection Site Haematoma, and Injection Site Swelling.*

